## Abstract

**Background:** Emergency conditions such as severe diarrhea, dyspnea, and seizures remain major causes of morbidity and mortality in low- and middle-income countries. Despite available World Health Organization (WHO) and national guidelines, adherence in rural outpatient departments (OPDs) is often suboptimal. The Organization for the Advancement and Support of Emergency Systems (OASES) App is a clinical decision-support system (CDSS) developed in 2025 by the University of Milano-Bicocca as part of a quality improvement collaboration with [name] Hospital, Kalongo, Uganda. The App digitizes validated WHO-based triage and emergency care algorithms for offline use in resource-limited hospitals, but it has not yet undergone formal testing and evaluation by intended end-users.

**Objective:** To evaluate the effectiveness, usability, and feasibility of the OASES App among frontline clinicians during simulated emergency scenarios.

**Methods:** This pilot study will employ a prospective, randomized, stratified crossover simulation design at [name] Hospital. Approximately 16 OPD clinicians (nurses, clinical officers, nursing assistants) will complete 12 facilitator-led standardized scenarios (diarrhea, dyspnea, seizures), randomized between App-assisted and standard practice conditions with a  $\geq 7$ -day washout. Primary outcome is clinicians' adherence to evidence-based guidelines for diagnostics and treatments. Secondary outcomes include triage accuracy, diagnostic accuracy, disposition decision appropriateness, process quality, case completion time, and user perceptions of usability, trust, and feasibility. Quantitative data will be analyzed using mixed-effects models, while qualitative feedback will undergo thematic analysis.

**Expected Outcomes:** Findings will provide preliminary evidence on the effectiveness and acceptability of the OASES App, inform App refinement, and support the design of a subsequent powered clinical evaluation.

## **A. Background and Rationale**

Emergency conditions such as severe diarrhea, dyspnea, and seizures remain leading causes of morbidity and mortality in low- and middle-income countries (LMICs). Despite the availability of World Health Organization (WHO) and national guidelines, the delivery of evidence-based emergency care is often suboptimal, particularly in rural and remote areas where limited training, high workload, and supply-chain constraints undermine adherence to recommended practices.

Mobile health (mHealth) innovations, including digital clinical decision-support systems (CDSS) delivered via smartphones and tablets, offer a promising means of bridging these implementation gaps. However, evidence regarding their effectiveness in rural emergency departments is scarce, with most interventions implemented at small scale and rarely subjected to rigorous evaluation. Simulation-based studies provide a safe, controlled environment in which to test digital tools, allowing systematic assessment of clinical performance, usability, and feasibility before clinical deployment.

The Organization for the Advancement and Support of Emergency Systems (OASES) App is a CDSS developed in 2025 by the University of Milano-Bicocca. Its development was undertaken as part of a broader quality improvement collaboration between the University of Milano-Bicocca and [name] Hospital, aimed at strengthening emergency and acute care services in rural Uganda. The App is an intuitive, tablet-based system that digitalizes validated triage and emergency care algorithms derived from WHO frameworks. Designed for offline use in hospitals with limited infrastructure, it guides frontline clinicians, particularly those with limited training, through systematic triage, diagnosis, and treatment steps for common emergency presentations in real time, while simultaneously collecting structured clinical data. The current version of the App includes a triage algorithm based on the Interagency Integrated Triage Tool (IITT) and three condition-specific modules for the management of diarrhea, dyspnea, and seizures in both adults and children. To date, the OASES App has not been tested in clinical or simulated settings. Prior to implementation in rural emergency departments, it therefore requires rigorous evaluation in simulation to determine its effectiveness, usability, and feasibility among intended end-users.

## **B. Study Objectives**

### Primary Objective:

- To determine whether the OASES App improves clinicians' adherence to evidence-based guidelines for the management of diarrhea, dyspnea, and seizures during simulated emergency scenarios.

### Secondary Objectives:

- To assess the effect of the OASES App on triage accuracy, disposition appropriateness, and diagnostic accuracy in simulated emergency scenarios.
- To evaluate whether the OASES App improves clinicians' adherence to guideline-recommended history taking and physical examination (process quality).
- To compare time to completion of simulated cases between App-assisted and standard practice arms.
- To evaluate usability, perceived usefulness, trust, satisfaction, and feasibility of the App.
- To explore potential learning and carryover effects associated with App use.

## **C. Methods**

### **C.1. Study Design**

This study will use a prospective, randomized, stratified crossover simulation design, conducted over a two-week period at [name] Hospital, Kalongo. Each participant will complete standardized simulation scenarios under two conditions: standard practice (control) and App-assisted practice (intervention). A washout period of at least seven days will separate the two conditions to minimize potential learning and carryover effects.

## **C.2. Setting**

[name] Hospital is a private, non-profit general hospital located in Kalongo Town Council, Agago District, Northern Uganda. The outpatient department (OPD) is the first point of contact for patients seeking care and has a dual role, providing both primary and emergency services. Simulations will be conducted in repurposed OPD consultation rooms to maintain ecological validity while minimizing disruption to routine clinical activities.

The study is part of a broader quality improvement collaboration between the University of Milano-Bicocca and [name] Hospital, which aims to strengthen emergency and acute care services in rural Uganda. This collaboration provides an appropriate and relevant context for evaluating the OASES App in a setting where it is intended to be implemented.

## **C.3. Participants**

This study will focus on frontline clinicians responsible for the initial assessment and management of patients in the OPD at [name] Hospital, where emergency care is primarily delivered by clinical officers, nurses, and nursing assistants.

### Inclusion Criteria:

- Nurses, clinical officers, or nursing assistants currently employed in the OPD of [name] Hospital.

### Exclusion Criteria:

- Individuals who are unable or unwilling to participate in both scheduled simulation sessions.

## **C.4. Sample Size**

This pilot study will use a feasibility-based sample size, determined by the total number of OPD clinicians available at [name] Hospital. We anticipate enrolling approximately 16 participants, representing all nurses, clinical officers, and nursing assistants currently working in the OPD of [name] Hospital. Each participant will complete 12 simulated scenarios, yielding an estimated 192 scenario-level observations. While not powered to detect small effect sizes, this sample is deemed to be sufficient to assess feasibility, refine study procedures, and provide preliminary effect estimates to inform the design and power calculations of a subsequent larger trial.

## **C.5. Recruitment and informed consent**

Recruitment will be conducted among OPD staff at [name] Hospital. The study will be introduced by the research staff during short informational meetings with staff, and a brief announcement will also be shared in an existing WhatsApp group used for communication between researchers of the University of Milano-Bicocca and the OPD staff (**Appendix A**). Interested individuals will then be approached privately and provided with detailed study information. Written informed consent will be obtained before starting any study procedure.

## **C.6. Randomization and allocation**

Participants will be randomized to the order of study conditions—App-assisted (intervention) vs. standard practice (control)—using computer-generated permuted blocks of size 2, stratified by cadre (nurse/nursing assistant vs clinical officer) to ensure balance across professional groups. The randomization list will be computer-generated in advance by a member of the research team not involved in recruitment or outcome assessment and stored in a password-protected master sheet. Participant IDs will be assigned sequentially after written consent in order of recruitment; each ID is then linked to a pre-specified condition sequence from the master sheet.

To control for case content and ordering effects, matched scenario pairs were created for each condition (A-set for one period, B-set for the other period), with random assignment of A vs. B to the first or second period per participant. Within each period, the case order (1–6) was independently randomized. Thus, for every participant the master sheet specifies: (i) intervention sequence, (ii) period assignment of A vs. B cases, and (iii) the randomized within-period case order.

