### C.8. Simulation and Scenarios

Each participant will complete 12 facilitated clinical vignette scenarios, with six scenarios per study arm (two diarrhea, two dyspnea, and two seizures). Scenarios will be adapted from WHO training materials for emergency care (e.g., *Basic Emergency Care* course, *Emergency Triage Assessment and Treatment* guidelines) and tailored to reflect common emergency presentations in the OPD of [name] Hospital. Both adult and pediatric cases will be included, varying in severity and presentation to capture the spectrum of conditions typically encountered. Draft cases will undergo expert review and pilot testing with representative clinicians to ensure clarity, realism, and contextual relevance. Cases will be designed in matched pairs to ensure comparable content and difficulty between study periods, with equivalence determined by expert review and pilot testing. Scenarios will be balanced for complexity, number of critical actions, and expected completion time.

Cases will be delivered verbally by a trained facilitator, who will respond only to participant questions to simulate real-world information gathering. Facilitators will log which key history and examination items are elicited using a structured tick-box script.

At two predefined points in each vignette, participants will record their diagnostic and treatment plan:

1. Initial assessment stage – working impression, immediate treatments, and diagnostic tests ordered.
2. Post-investigation stage – final diagnosis, disposition decision, treatment plan and follow-up plan.

Each participant's simulation session will last approximately one hour. All sessions will be scheduled during off-duty hours to ensure voluntary participation and to avoid disruption of patient care.

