### C.11. Statistical Analysis

All analyses will follow the intention-to-treat principle. For vignette-level outcomes, if a participant does not complete an entire scenario, that scenario will be excluded from analysis. Within completed scenarios, missing or blank responses will be treated as incorrect (i.e., non-adherent), on the assumption that an unanswered item reflects lack of knowledge or failure to act. For survey outcomes, only available responses will be analyzed, with no imputation. Descriptive statistics will therefore be based on the number of participants who provided a response to each item. The number of missing scenarios and survey responses will be reported.

The primary analysis will follow a crossover design, with each participant contributing observations under both study conditions (App-assisted vs. control) across distinct but content-equivalent case scenarios:

- Guideline-adherent management: Analyzed as a bounded proportion (0-1) using a generalized linear mixed-effects model with binomial distribution and logit link. The model will include fixed effects for study arm (App vs. control), period (first vs. second session), sequence (allocation order), scenario type (diarrhea, dyspnea, seizure), cadre (clinical officers vs nurses), years of experience (continuous), baseline comfort in using mobile Apps (dichotomous). Random intercepts will be specified for participant to account for repeated measures. Results will be reported as adjusted mean differences with 95% CIs. Inter-rater reliability will be assessed using Cohen's  $\kappa$  for individual items and intraclass correlation coefficients (ICC) for total checklist scores.
- Triage appropriateness, disposition appropriateness, and diagnostic accuracy: Each will be analyzed as binary outcomes (correct vs. incorrect) using mixed-effects logistic regression, with the same fixed and random effects structure as above. Results will be reported as adjusted odds ratios with 95% CIs. Inter-rater agreement will be evaluated using Cohen's  $\kappa$ .

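### Case set (A or B) is randomised per participant but has no term in the C.11 model, so a chance imbalance of sets between arms adds error to the App effect that the planned confidence interval does not reflect

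*Combined protocol and SAP*

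**What the plan says.** Section C.6 randomises treatment order "using computer-generated permuted blocks of size 2, stratified by cadre". It then creates matched A and B case sets, "with random assignment of A vs. B to the first or second period per participant", and adds a third element: "Within each period, the case order (1–6) was independently randomized". The master sheet lists treatment order, period of each set and case order as three separate items. Blocking is described for treatment order only, and nothing is said about balancing set within sequence.

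Section C.8 gives "six scenarios per study arm (two diarrhea, two dyspnea, and two seizures"). It plans matched pairs, aims to even out difficulty, number of critical actions and duration, and leaves the judgement of equivalence to experts and a pilot. No numerical criterion is given.

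Section C.11 specifies "fixed effects for study arm (App vs. control), period (first vs. second session), sequence (allocation order), scenario type (diarrhea, dyspnea, seizure"), plus cadre, years of experience and comfort with apps, and a random intercept for participant. Neither set nor case appears. The models for triage, disposition, diagnosis and process quality reuse this structure.

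**The concern.** For any one participant, set is completely tied to arm: all App cases come from one set and all control cases from the other. Set therefore acts on the within-person comparison just as period does, yet only period is modelled. No listed term can stand in for it. Scenario type cannot, because each set holds two cases of every type. Period and sequence cannot, because set is drawn per participant and is not fixed by either.

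If one set proves harder and happens to fall more often under one arm, part of that difference is read as an App effect, in either direction. The model also leaves this source of variation out of its standard error, so the interval is too narrow. C.11 names this crossover analysis of the primary outcome as the only confirmatory one, and C.4 intends its estimate to inform the power calculation of a larger trial.

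**Working it through.** **Inputs from the documents.** C.4: "We anticipate enrolling approximately 16 participants" and "Each participant will complete 12 simulated scenarios, yielding an estimated 192 scenario-level observations". The plan's own figure reproduces: 16 × 12 = 192. It states no power, effect size or standard deviation, so there is nothing further to reproduce.

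**Assumptions, not in the documents.** Eight participants per sequence; independent 50:50 set draws; a gap d between the sets in mean adherence of 0 to 15 points; for the simulation, mean adherence 0.5, participant SD 0.5 on the logit scale, and 3 or 6 scored items per vignette. Three items correspond to the boxes on the Appendix E assessor sheet that concern tests and treatments, which is how C.9 defines the primary outcome. Six is the whole sheet, including triage, diagnosis and disposition, which C.9 treats as secondary.

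**Step 1: imbalance.** Let k be the number of participants with set A under the App. The App-minus-control difference in the share of sessions on set A is (2k − 16)/16, with k ~ Binomial(16, 0.5).

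- SD = √16/16 = 0.25.
- Exact balance (k = 8): 12,870/65,536 = 19.6%.
- Split 11–5 or worse (imbalance at least 6/16 = 0.375): 2 × P(k ≤ 5) = 21.0%.
- Split 12–4 or worse (at least 8/16 = 0.50): 2 × P(k ≤ 4) = 7.7%.

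**Step 2: error in the App effect.** Error = imbalance × d, with mean 0 and SD 0.25 × d.

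| Assumed gap d (points) | Error SD (points) | Error at 11–5 | Error at 12–4 |
|---|---|---|---|
| 5 | 1.25 | 1.875 | 2.5 |
| 10 | 2.5 | 3.75 | 5 |
| 15 | 3.75 | 5.625 | 7.5 |

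**Step 3: effect on the test.** Trials with no App effect were simulated (1,000 per setting) and analysed by a binomial logit model with arm, period, scenario type and participant indicators in place of the random intercept.

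| Gap d (points) | No set term, 3 items | No set term, 6 items | With set term, 3 / 6 items |
|---|---|---|---|
| 0 | 3.9% | 4.9% | 4.2% / 4.2% |
| 5 | 6.6% | 6.8% | 5.3% / 4.6% |
| 10 | 8.6% | 15.0% | 5.4% / 5.9% |
| 15 | 14.2% | 21.8% | 5.9% / 6.8% |

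Monte Carlo error is about 1 point.

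**Step 4: check by hand.** With 3 items and no set term, the mean model SE stays at about 0.0437 whatever the gap. At d = 10 points the true spread should be √(0.0437² + 0.025²) = 0.0503, which is the simulated value. The rejection rate should be P(|Z| > 1.96 × 0.0437/0.0503) = P(|Z| > 1.70) ≈ 8.9%, against 8.6% simulated.

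**Step 5: the first-period analysis.** With eight participants per arm, the set imbalance between arms has SD √(0.25/8 + 0.25/8) = 0.25. Restricting to the first period therefore gives no protection.

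**The case against.** The best defence is that set was itself randomised and the cases were matched. Both parts have force. A reader might infer that omitting set biases the App effect. The documents do not support that: the error averages zero over randomisations, and what remains is chance error in the one trial run, plus understated uncertainty. If the matching works, d is small; at 5 points or less the error SD is at most 1.25 points and type I error about 7%. But the matching rests on judgement, and a model without a set term cannot check it.

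A reader might also take it as established that the sets are unbalanced. C.6 implies independent draws but does not say so; if the master sheet balances set within sequence, the problem largely disappears.

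The 6-item figures should not be the headline, because they count items outside the primary outcome as C.9 defines it.

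Three further inferences fail:

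- Leaving out case position does not confound the App effect, since every participant goes through positions 1 to 6 once in each arm.
- It does not follow that the learning objective goes unanswered. That objective is only "To explore potential learning and carryover effects associated with App use", and the plan has period and sequence terms and a first-exposure analysis.
- The block size of 2 is a separate matter. Fixed blocks of 4 would also leave some allocations predictable.

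That this is a feasibility-sized pilot lowers the stakes, but not the case for a term that costs one degree of freedom.

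**Conclusion.** The point holds as a gap in the analysis model. The plan randomises a factor that is tied to arm within each participant, states no balancing of it, and then leaves it out of every vignette-level model. The likely size is modest: with three items per vignette, type I error of about 6.6% to 14% for assumed gaps of 5 to 15 points. It could be nil if the sets are equally hard or the list is balanced. These figures rest on 16 participants, independent 50:50 set draws, a gap that the documents do not give, and otherwise ideal binomial data. The change should be made because it is cheap and uses a factor that the trial already randomises; the omission is not fatal to the trial.

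**What to change.** - Add case set (A vs B) as a fixed effect in every vignette-level model in C.11, including the time model and the first-period sensitivity analysis. Case ID is an alternative. It is recorded on the forms in Appendices C, D and E, so no new data are needed.
- Report the sequence-by-set table and the estimated set effect, so that readers can see both the imbalance and the gap.
- State in C.6 whether the master sheet balances set within sequence. If the list is not yet in use, balance it so; with the four combinations equal, the imbalance is zero by design.
- A case-position term is optional and exploratory.

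**Cost.** One degree of freedom and a line of text. If the sets are in fact equal, the standard error grows by about 3–4% on average (simulated: 0.0456/0.0437 = 1.043 with 3 items, 0.0318/0.0306 = 1.039 with 6). The variance factor is 1/(1 − imbalance²). At an 11–5 split this is 1.16, or √1.16 ≈ 1.08 on the standard error (8% larger); at 12–4 it is 1.33, or √1.33 ≈ 1.15 (15% larger).

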### C.7. Intervention and Control

Experimental arm (OASES App): Participants will use the OASES tablet-based CDSS, which incorporates the Interagency Integrated Triage Tool (IITT) and three condition-specific algorithms (diarrhea, dyspnea, and seizures) derived from WHO and Uganda Clinical Guidelines. No formal training sessions will be conducted; however, participants will receive a brief orientation walk-through of the App immediately prior to its use.

Control arm (standard practice): Participants will manage simulated cases without the App, relying on their usual knowledge and clinical experience. Standard resources available in OPD, including paper-based versions of the IITT and Uganda Clinical Guidelines, will be available for reference.

All participants will complete both arms using a crossover design, with a washout period of at least one week between conditions. During the washout, participants will return to their normal OPD duties without access to the OASES App. No additional clinical teaching or training will be provided during the study period.

### C.8. Simulation and Scenarios

Each participant will complete 12 facilitated clinical vignette scenarios, with six scenarios per study arm (two diarrhea, two dyspnea, and two seizures). Scenarios will be adapted from WHO training materials for emergency care (e.g., *Basic Emergency Care* course, *Emergency Triage Assessment and Treatment* guidelines) and tailored to reflect common emergency presentations in the OPD of [name] Hospital. Both adult and pediatric cases will be included, varying in severity and presentation to capture the spectrum of conditions typically encountered. Draft cases will undergo expert review and pilot testing with representative clinicians to ensure clarity, realism, and contextual relevance. Cases will be designed in matched pairs to ensure comparable content and difficulty between study periods, with equivalence determined by expert review and pilot testing. Scenarios will be balanced for complexity, number of critical actions, and expected completion time.

Cases will be delivered verbally by a trained facilitator, who will respond only to participant questions to simulate real-world information gathering. Facilitators will log which key history and examination items are elicited using a structured tick-box script.

At two predefined points in each vignette, participants will record their diagnostic and treatment plan:

1. Initial assessment stage – working impression, immediate treatments, and diagnostic tests ordered.
2. Post-investigation stage – final diagnosis, disposition decision, treatment plan and follow-up plan.

Each participant's simulation session will last approximately one hour. All sessions will be scheduled during off-duty hours to ensure voluntary participation and to avoid disruption of patient care.

